8.4 Estimation Methods

Model parameters will be estimated in a Bayesian statistical framework using Markov Chain Monte Carlo sampling for inference [2]. Advantages of the Bayesian framework include the ability to express analysis results in terms of clinically relevant probabilities and the ability to perform exact inference on complicated functions of model parameters, for example, the win ratio.

Prior distribution

Bayesian analysis requires the specification of a probability distribution representing prior information about the set of unknown model parameters before observing the study data. Because no single choice of prior can accurately capture the viewpoints of all potential stakeholders, the analysis will be performed with multiple choices for the prior distribution. For the primary analysis, the prior for treatment main and interaction effects will be a set of independent normal distributions:

$$\begin{aligned}\mu &\sim N(\text{mean} = 0, \text{SD} = 0.3537) \quad (\text{main effect}) \\ \gamma_1 &\sim N(\text{mean} = 0, \text{SD} = 0.3537) \quad (\text{main effect}) \\ \gamma_2 &\sim N(\text{mean} = 0, \text{SD} = 0.3537) \quad (\text{main effect}) \\ \delta_1 &\sim N(\text{mean} = 0, \text{SD} = 0.2651) \quad (\text{interaction}) \\ \delta_2 &\sim N(\text{mean} = 0, \text{SD} = 0.2651) \quad (\text{interaction})\end{aligned}$$

The main effects SD = 0.3537 was chosen to imply that odds ratios for HCQ versus no HCQ and AZM versus no AZM are between 0.5 and 2.0 with 95% probability assuming that the interaction effects are zero. The interaction SD = 0.2651 was chosen to imply that the ratio of odds ratios for HCQ versus no HCQ across two levels of AZM and the ratio of odds ratios for AZM versus no AZM across two levels of HCQ would each be between 0.8 and 1.25 with 80% probability. The intercept parameters θ_k will be assigned central t distributions with 3 degrees of freedom and SD = 10 subject to the constraint $\theta_0 < \theta_2 < \dots < \theta_7$, which is the default prior in the R package 'brms'. To explore sensitivity to the choice of prior, the analysis will be repeated using two alternative forms for the prior distribution. The first alternative prior distribution will be the same as above but will set $\delta_1 = \delta_2 = 0$ with 100% probability. The second alternative prior will assign a non-informative improper uniform distribution to the set of main effects and interaction terms. Additional prior distributions may be implemented post-hoc for manuscript presentations or by request of external reviewers and stakeholders.

Computation

Posterior means and credible intervals for the Win Ratio quantities of interest will be calculated using Hamiltonian Markov Chain Monte Carlo (MCMC) simulations as implemented in the R package 'brms'. [4,4] To reduce Monte Carlo error, we will generate a large number of simulated parameter values and will perform graphical and other diagnostic checks to ensure convergence. To perform inference on Win-Ratio^{HCQ} and Win-Ratio^{AZM} we note that each of these quantities is a function of the cell probabilities $\boldsymbol{\pi}$ defined in Table 3 which in turn are functions of the model parameters $\Theta = (\theta_0, \theta_1, \theta_2, \theta_3, \theta_4, \theta_7, \theta_6, \theta_7, \mu, \gamma_1, \gamma_2, \delta_1, \delta_2)$. We use notation Win-Ratio^{HCQ}(Θ) and Win-Ratio^{AZM}(Θ) to denote the value of the win ratios as a function of unknown model parameters. Posterior mean point estimates of the win ratios will be calculated as

$$\begin{aligned}\widehat{\text{Win-Ratio}}^{\text{HCQ}} &= \frac{1}{M} \sum_{i=1}^M \text{Win-Ratio}^{\text{HCQ}}(\Theta^{(i)}) \\ \widehat{\text{Win-Ratio}}^{\text{AZM}} &= \frac{1}{M} \sum_{i=1}^M \text{Win-Ratio}^{\text{AZM}}(\Theta^{(i)})\end{aligned}$$

where M is the number of MCMC iterations and $\Theta^{(i)}$ is the simulated value of Θ on the i -th iteration of the MCMC procedure. A 95% credible for the win ratios will be obtained by calculating the 2.5th and 97.5th empirical percentiles of the quantities Win-Ratio^{HCQ}($\Theta^{(i)}$) and Win-Ratio^{AZM}($\Theta^{(i)}$) across the M simulated values. Finally, the probability that each win ratio falls above or below a clinically relevant threshold will be calculated by counting the proportion of simulated win ratio values that fall above or below the threshold.

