8.7 Exploratory Pairwise Group Comparisons

The treatment effects estimated by the primary analysis are averages in the sense that the comparison of HCQ versus no HCQ is aggregated over AZM subgroups and the comparison of AZM versus no AZM is aggregated over HCQ subgroups. The primary reason for targeting average as opposed to subgroup-specific treatment effects which are potentially more informative for practice is the expected lack of statistical precision for estimating subgroup-specific effects. In order to shed light on potential treatment effect heterogeneity across AZM and HCQ subgroups, we will report estimated odds ratios and accompanying 95% credible intervals comparing treatment groups on a pairwise basis from the primary analysis proportional odds model.

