9 ANALYSIS OF SECONDARY EFFICACY ENDPOINTS

The major treatment group comparisons of HCQ versus no HCQ and AZM versus no AZM will be repeated using the following secondary clinical endpoints in place of the primary endpoint:

- Mortality during the index hospitalization
- Number of days on mechanical ventilation during the index hospitalization
- Progression to mechanical ventilation during index hospitalization.
- Day 28 WHO ordinal scale
- Days from randomization until hospital discharge
- Duration of fever after randomization
- Duration of supplemental oxygen use after randomization

Analysis of **index hospitalization mortality status** and **mechanical ventilation** will be performed using logistic regression. The analysis will use the same predictors as the primary endpoint proportional odds model and will use the same Bayesian prior distribution for the main effects and interaction effects parameters. For the ventilation endpoint, patients on ventilator at baseline will be excluded. To facilitate interpretation, parameter estimates from the logistic regression model will be re-expressed as win ratios, risk ratios, and/or risk differences.

Analysis of the **day 28 WHO scale** will be identical to the primary endpoint analysis using the day 28 assessment in place of the 14 day assessment.

Analysis of **length of hospital stay, duration of fever, and duration of supplemental oxygen use** will be based on a continuation ratio model for discrete time-to-event data treating death as a competing risk. For length of stay, the continuation ratio approach models that probability of being discharged on day $d + 1$ conditional on being alive and in-hospital on day d and assumes that covariates have a multiplicative effect on this probability. For patients who die prior to discharge, the patient's discharge date will be set to the last date of the patient's potential follow-up time. The interpretation is similar for duration of fever and supplemental oxygen. Predictor variables in the continuation ratio model will be identical to the primary endpoint proportional odds model and will use a similar prior distribution for the main effects and interaction terms.

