11 INTERIM ANALYSES

The primary objective of interim analyses is to ensure the safety of the participants enrolled in the trial and to evaluate the accumulating safety and efficacy data by treatment group to test for possible differences favoring any of the randomized treatments or treatment combinations. In addition, interim monitoring will involve a review of participant recruitment, compliance with the study protocol, status of data collection, an assessment of whether control group event rates are consistent with the rates hypothesized in the sample size calculations, and other factors which reflect the overall progress and integrity of the study including potential geographic differences.

An independent DSMB will review safety data on a regular basis according to the schedule specified in the DSMC charter. A team of one or two independent statisticians (i.e., the DSMB reporting statisticians) will be the only individuals (aside from the DSMB) with knowledge of interim outcomes by treatment group. Safety listings and tabular summaries will be generated regularly for the DSMB review. Unplanned meetings may be called if the DSMB members deem it to be necessary. The frequency of generating/sending these tables and listings to the DSMB is specified in the DSMC Charter.

Interim efficacy analyses will focus on the primary endpoint (World Health Organization ordinal scale) and death during the index hospitalization. Analyses will be performed both for the comparison of hydroxychloroquine versus no hydroxychloroquine (Hypothesis #1) and for the comparison of azithromycin versus no azithromycin (Hypothesis #2). The first pre-planned interim review of efficacy data will be performed after completion of data collection for the primary endpoint of the first 75 participants and subsequent pre-planned efficacy reviews will be performed approximately bi-weekly or based on a schedule specified in the DSMB charter. Considerations for multiple testing of the accumulating trial data are discussed in Section 11.1.

Statistical methods for interim analyses will be identical to those described in Section 8 for the final analysis. For the WHO scale primary endpoint, the statistical framework will be a Bayesian parametric win ratio analysis based on the proportional odds model. For mortality, the statistical framework will be a Bayesian logistic regression analysis. Guidelines proposed to the DSMB for interpretation of interim results are summarized in Table 5:

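### The interaction prior SD of 0.2651 puts 60%, not the stated 80%, of its probability on ratios of odds ratios between 0.8 and 1.25

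*SAP*

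**What the plan says.** In SAP section 8.4 (Prior distribution), "the prior for treatment main and interaction effects will be a set of independent normal distributions": mean 0 and SD 0.3537 for μ, γ1 and γ2, and mean 0 and SD 0.2651 for the interactions δ1 and δ2. The text then justifies both constants.

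- Main effects: the SD was chosen so that the HCQ and AZM odds ratios "are between 0.5 and 2.0 with 95% probability assuming that the interaction effects are zero".
- Interactions: "The interaction SD = 0.2651 was chosen to imply that the ratio of odds ratios for HCQ versus no HCQ" across two AZM levels, and the corresponding ratio for AZM across two HCQ levels, "would each be between 0.8 and 1.25 with 80% probability".

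The interaction prior is used beyond the primary model fit. Section 8.7 takes pairwise contrasts from that model: "we will report estimated odds ratios and accompanying 95% credible intervals comparing treatment groups on a pairwise basis". Section 9 says that the logistic models for in-hospital mortality and mechanical ventilation "will use the same Bayesian prior distribution for the main effects and interaction effects parameters". Section 11 says: "Statistical methods for interim analyses will be identical to those described in Section 8 for the final analysis".

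**The concern.** The constant and the sentence that justifies it cannot both be right. The sentence is the only place where a reader learns, in interpretable terms, how sceptical the primary prior is about interaction. If the SD is as printed, the prior is less sceptical than the sentence claims. If the sentence states the intent, the SD is about 1.5 times too large (0.2651/0.1741 = 1.52).

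This matters in a plan that makes no multiplicity adjustment and relies, in section 11.1, on a prior calibrated to the reader's scepticism. That passage concerns treatment benefit or harm rather than interaction, so the point should not be overstated. Still, the interaction prior controls how far the stratum-specific odds ratios are pulled towards a common value, and these are the results that section 8.7 offers as evidence on heterogeneity.

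**Working it through.** **Inputs** (all from SAP section 8.4): δ ~ N(0, 0.2651) on the log odds ratio scale; interval 0.8 to 1.25; stated probability 80%; main-effect SD 0.3537 with interval 0.5 to 2.0 and stated probability 95%. By the model in section 8.3, exp(δ1) and exp(δ2) are the ratios of HCQ odds ratios in the AZM and AZM-ineligible strata relative to no AZM.

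**1. The plan's method, checked on the main effect.** SD = ln 2 / z(0.975) = 0.69315/1.95996 = 0.35365, and SD 0.3537 gives 2Φ(ln 2/0.3537) − 1 = 0.950. The stated 95% is reproduced, as a two-sided central probability.

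**2. The same method on the interaction.** Because ln 0.8 = −ln 1.25, the interval is symmetric on the log scale.

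- ln 1.25 = 0.22314, and 0.22314/0.2651 = 0.8417.
- P(0.8 < exp(δ) < 1.25) = 2Φ(0.8417) − 1 = 0.600, against the stated 0.80.
- SD needed for 80%: 0.22314/z(0.90) = 0.22314/1.28155 = 0.1741.
- Central 80% range with SD 0.2651: exp(±1.28155 × 0.2651) = 0.71 to 1.40.
- Variance ratio: (0.2651/0.1741)² = 2.3.

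**3. Other readings.**

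| Reading | Probability |
|---|---|
| δ1 or δ2, two-sided | 60.0% |
| δ2 − δ1 (AZM-ineligible against AZM), SD 0.2651 × √2 = 0.3749 | 44.8% |
| 0.2651 taken as a variance | 33.5% |
| One-sided, P(ratio < 1.25) | 80.0% |

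Only the one-sided reading gives 80%, and a range with two limits is not one-sided. Also, 0.22314/z(0.80) = 0.22314/0.84162 = 0.2651, so the 80th percentile was probably used where the 90th was needed. That is an inference, since the SAP shows no derivation.

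**4. Effect on the prior for a stratum-specific HCQ odds ratio** (group 4 vs 3 or 6 vs 5, which is μ + δ):

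| Interaction SD | SD of μ + δ | 95% range of odds ratio | P(0.5 to 2.0) |
|---|---|---|---|
| 0.2651 | √(0.3537² + 0.2651²) = 0.4420 | 0.42 to 2.38 | 88.3% |
| 0.1741 | √(0.3537² + 0.1741²) = 0.3942 | 0.46 to 2.17 | 92.1% |

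**5. Illustration of the effect on estimates.** The SAP gives neither the share of AZM-ineligible patients nor the outcome distribution, so these figures rest on assumptions: a normal approximation to the six-group model, V = (X′DX + P)⁻¹, with D the group size times information per patient and P the prior precisions; 20–40% AZM-ineligible; information 0.20–0.33 per patient; equal allocation within strata. N = 500 is the number used in the section 11.1 simulation, and N = 75 is the first efficacy review. The retention and estimate rows take a true δ1 of ln 1.5 with all other effects null.

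| Quantity | SD 0.2651 | SD 0.1741 |
|---|---|---|
| Share of δ1 retained, log scale, N = 500 | 33–46% | 18–27% |
| Expected odds ratio, group 4 vs 3 (true 1.5), N = 500 | 1.23–1.30 | 1.17–1.24 |
| Posterior SD, group 4 vs 3, N = 500 | 0.193–0.245 | 0.174–0.216 |
| Posterior SD, averaged HCQ, N = 75 | 0.273–0.304 | 0.269–0.298 |
| Posterior SD, averaged AZM, N = 75 | 0.281–0.318 | 0.276–0.310 |

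At N = 500 the averaged posterior SDs differ by at most about 0.001 (HCQ) and 0.002 (AZM). The averaged AZM effect here is the contrast that section 8.2 describes in words (3 vs 1 and 4 vs 2).

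**The case against.** The strongest reply is that the analysis itself is not ambiguous. Section 8.4 prints the SD, so two analysts would fit the same model, and a careful reader can work out the 60%. The averaged effects are almost unchanged, and Table 5 monitors only those, so the interim rules are barely touched. The visible effect is on results labelled exploratory, for which section 8.7 already expects poor precision and sets no threshold. Section 8.4 also plans one analysis with δ fixed at 0 and another with a flat prior, and section 8.3 says that the sample size calculations omitted interactions, so those cannot have depended on 0.2651.

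Most of this stands, and it limits the weight of the point. It does not remove the contradiction: printing the SD shows what will be run, not whether that is what was meant. The two sensitivity priors lie on either side of both SDs for the interaction, but the flat one also flattens the main effects. It therefore does not isolate the interaction SD, and neither analysis corrects the sentence. The illustration rests on assumed inputs and should not carry the conclusion, which needs only the 60% against 80%.

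**Conclusion.** The statement is wrong as written. Stated 80%, actual 60.0%; this is exact and uses only the SAP's own figures. It is not a rounding matter, because 80% needs an SD of 0.1741. The document does not show whether the SD or the probability reflects the intent.

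The averaged HCQ and AZM conclusions are not at risk. Under the stated assumptions, the material effect is on the exploratory stratum-specific odds ratios, whose posterior SD (group 4 vs 3) is 11–14% larger with 0.2651 than with 0.1741 at N = 500. The point should be corrected because it concerns a constant in the primary-analysis prior that is reused in sections 9 and 11, and because the correction is cheap.

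**What to change.** Reconcile the constant and the sentence in section 8.4 before outcome data are examined; the first efficacy review is at 75 participants, and a later choice of SD could look data-driven. Either:

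- **Keep 0.2651** and restate the probability as 60% for 0.8 to 1.25, or equivalently 80% for 0.71 to 1.40. Cost: one sentence, no change to code.
- **Change the SD of δ1 and δ2 to 0.1741** in the prior specification, in the sentence that justifies it and in the code. Cost: one constant, plus a rerun of any simulation that used 0.2651. The sample size calculations are not affected, since they set δ1 = δ2 = 0. The simulation behind the 14% in section 11.1 may be, because its prior is not stated.

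In either case, state which interaction SD, if any, the pre-trial simulations used. Sections 9 and 11 refer back to this prior, so correcting it once at its source is enough.

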8.5 Secondary Analyses of the Primary Endpoint

The primary analysis is unadjusted for baseline covariates but a covariate-adjusted analysis will also be presented for the major hypotheses in order to target a potentially more clinically relevant treatment effect estimand. Baseline covariates for this analysis will include ventilator status at the time of

randomization and enrolling site. To implement the covariate-adjusted analysis, baseline ventilator status and site will be included as main effects covariate adjustments in the proportion odds model along with the set of treatment group indicators used in the primary analysis. Win ratios for HCQ and AZM will be defined in a manner analogous to the primary analysis. The covariate-adjusted win ratio for HCQ will be a comparison between a hypothetical randomly selected patient from one of the HCQ groups (2, 4, or 6) and a hypothetical randomly selected patient from the same site, same baseline ventilator status, and same AZM subgroup who was randomized to no HCQ. The covariate-adjusted win ratio for AZM will be a comparison between a hypothetical randomly selected patient from one of the AZM groups (3 or 4) and a hypothetical randomly selected patient from the same site, same baseline ventilator status, and same HCQ subgroup who was randomized to no AZM.

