4 RANDOMIZATION METHODOLOGY

Patients meeting entry criteria will be stratified by eligibility to undergo randomizations for both study drugs or only HCQ.

Stratum 1: Eligible for both study drugs

Participants who are eligible for both study drugs will be randomized in a 1:1:1:1 ratio to one of the following:

Group	Description
-------	-------------

1	Standard of Care
2	Standard of Care + HCQ
3	Standard of Care + AZM
4	Standard of Care + HCQ + AZM

Stratum 2: Ineligible for azithromycin

Participants who are ineligible to be randomized to azithromycin will be randomized in a 1:1 ratio to one of the following groups

Group	Description
5	Standard of Care --
6	Standard of Care + HCQ

Randomizations within each stratum will use permuted blocks with random block sizes and will be further stratified by ventilator status at baseline.

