6 DESCRIPTION OF EFFICACY ENDPOINTS

6.1 Primary Endpoint

The primary outcome measure is the World Health Organization (WHO) ordinal scale for clinical improvement as measured on day 14 after randomization. The WHO scale has 9 levels numbered 0 to 8 with 0 denoting no clinical or virologic evidence of infection and 8 denoting death.

Table 2. World Health Organization ordinal scale for clinical improvement

Descriptor	Score
No clinical or virologic evidence of infection	0
No limitation of activities	1
Limitation of activities	2
Hospitalized, no oxygen therapy	3
Oxygen by mask or nasal cannula	4
Non-invasive ventilation or high-flow oxygen	5
Intubation and mechanical ventilation	6
Mechanical ventilation + additional organ support (pressors, renal replacement therapy, ECMO)	7
Death	8

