8.6 Contingency for Violation of Proportional Odds Assumption

The proportionality assumption underlying the proportional odds model will be assessed by examining plots of empirical cumulative logits across treatment groups and comparing observed versus model-predicted probabilities. If there is substantial evidence of an unacceptable degree of model misspecification (e.g. the empirical cumulative logits from different treatment groups are clearly crossing) then a nonparametric instead of parametric win ratio analysis will be presented. To implement a Bayesian nonparametric version of the win ratio analysis, cell probabilities underlying the win ratio calculation (Table 3) will be estimated empirically by assigning noninformative independent Dirichlet distributions to the set of category probabilities within each treatment group. Other details of the calculations are essentially identical to those described for the primary analysis. The prior for this nonparametric Bayesian analysis was chosen for simplicity and computational convenience and may be revised in a subsequent version of the Statistical Analysis Plan.

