11.1 Multiplicity considerations for interim analyses

The repeated analysis of multiple endpoints across multiple time points gives rise to the possibility of drawing an incorrect conclusion as a result of the play of chance. Based on Monte Carlo simulations performed during protocol development, we estimate that the probability of a signal occurring for moderate or any efficacy if outcomes are monitored continuously across 500 patients and there is truly no between group difference in the primary endpoint is 14%. The Bayesian approach to controlling the probability of an incorrect conclusion involves selecting a prior distribution that faithfully reflects the user's prior degree of skepticism concerning the possibility of a clinically meaningful treatment benefit or harm. If the Bayesian prior distribution is well calibrated to the user's degree of skepticism, then the calculated posterior probabilities are appropriate to use for decision making without the requirement for a multiple comparisons adjustment. Although we have specified a set of guidelines for monitoring by the DSMB, we do not specify a degree of Bayesian certainty that should be regarded as "definitive evidence" at the end of the trial. Instead, we assume that stakeholders will use the calculated probabilities to inform their decision making and that different users may apply different thresholds for determining whether the degree of certainty is sufficient to warrant any particular conclusion or action based on the data.

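### Randomization is stratified by baseline ventilator status but the primary and interim model omits it, so the posterior is too wide if ventilation is prognostic

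*SAP*

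**What the plan says.** - **Design.** Section 4, after splitting patients by azithromycin (AZM) eligibility: "Randomizations within each stratum will use permuted blocks with random block sizes and will be further stratified by ventilator status at baseline".
- **Primary model.** Section 8.3 has cut-points, a hydroxychloroquine (HCQ) effect, terms for AZM assignment and AZM ineligibility, and their interactions. One stratifier (AZM eligibility) is therefore modelled and the other (ventilator status) is not. Section 8.5 confirms this: "The primary analysis is unadjusted for baseline covariates but a covariate-adjusted analysis will also be presented for the major hypotheses". Ventilator status enters only that secondary analysis, together with site, and the reason given there is a different estimand.
- **Interim looks.** Section 11: "Statistical methods for interim analyses will be identical to those described in Section 8 for the final analysis". No adjusted interim analysis is named.
- **Secondary endpoints.** The Section 9 regression models, including the one for in-hospital mortality (the second interim endpoint), reuse the primary predictors. The exception that matters here is progression to ventilation: "For the ventilation endpoint, patients on ventilator at baseline will be excluded".
- **Use of results.** Section 11.1 sets no final threshold: "we assume that stakeholders will use the calculated probabilities to inform their decision making". Table 5 compares the posterior probabilities with fixed cut-offs.

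**The concern.** Blocked randomization within ventilator strata removes nearly all chance imbalance on that factor, so the treatment estimate varies less between repeated trials than it would under simple randomization. A model that leaves the factor out cannot see this and still counts the spread between ventilated and unventilated patients as random error. Section 6.1 makes "Intubation and mechanical ventilation" a level of the outcome itself, so prognostic value at day 14 is likely.

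The posterior probabilities are what this trial delivers. Section 11.1 defends the lack of a multiplicity adjustment on the ground that they can be taken at face value, and that also requires a likelihood that reflects the design. All Table 5 cut-offs exceed 50%, so an over-wide posterior suppresses every type of signal. For efficacy this means delay or a missed signal. For inefficacy and harm, being conservative does not protect participants.

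**Working it through.** **Inputs from the SAP.** Allocation 1:1:1:1 or 1:1 in permuted blocks (Section 4). Prior SDs 0.3537 for main effects and 0.2651 for interactions (Section 8.4). Efficacy signals if P(win ratio >1) >95% or P(win ratio ≥1.25) >80% (Table 5). First look at 75 participants (Section 11). A 14% chance of a false efficacy signal under continuous monitoring to 500 patients (Section 11.1).

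**Assumptions, because the SAP gives none of these.** Proportion ventilated, strength of the ventilator effect, outcome distribution, and share AZM-ineligible (20% unless stated).

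**1. The plan's own figure.** The main-effect prior reproduces: ln 2 / 1.96 = 0.3537. The score process was simulated with information n/4 × (1 − Σp³)/3, that prior, no interaction, no ventilator effect and both efficacy rules. A false signal occurred in 12–13% of trials, close to the stated 14%.

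**2. Analytic size.** Under stratified randomization and the null, the true variance of the unadjusted estimate is R times the model variance, where R = within-ventilator-stratum ridit variance / total ridit variance. Intervals are too wide by the factor 1/√R.

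| Ventilated | Ventilator log OR (absolute) | R | 1/√R |
|---|---|---|---|
| 20% | 1 / 2 / 3 | 0.95 / 0.84 / 0.72 | 1.03 / 1.09 / 1.18 |
| 40% | 1 / 2 / 3 | 0.93 / 0.75 / 0.57 | 1.04 / 1.15 / 1.32 |

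With R in place, the 12–13% of step 1 falls to 9% and 6% (20% ventilated, log OR 2 and 3) and to 7% and 3% (40%).

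**3. Six-group model.** N=500, 10,000 trials per scenario, blocks within AZM stratum by ventilator status. Assumed unventilated control distribution for levels 0–8: 5/35/20/10/12/6/4/2/6%. A normal approximation to the posterior was used, with the sign of the effect standing in for win ratio >1. Contrasts were μ + 0.4δ₁ + 0.2δ₂ for HCQ and γ₁ + 0.5δ₁ for AZM. The SE/SD column uses a flat prior under the null; the signal columns use the SAP prior and show unadjusted → adjusted.

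| Ventilated / log OR | SE/SD, unadjusted, HCQ | Signal at OR 1.5, HCQ | Signal at OR 1.5, AZM | Null signal, HCQ |
|---|---|---|---|---|
| 15% / −1.5 | 1.03 | 75% → 78% | 66% → 70% | 3.0% → 3.6% |
| 15% / −2.5 | 1.09 | 69% → 76% | 61% → 70% | 2.6% → 3.9% |
| 30% / −1.5 | 1.07 | 72% → 77% | 65% → 70% | 2.9% → 3.8% |
| 30% / −2.5 | 1.19 | 63% → 78% | 53% → 69% | 1.7% → 3.9% |

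Adjusted SE/SD is 0.99–1.00. Coverage of the 95% interval is 95.9–98.2% unadjusted and 94.7–95.1% adjusted. This fits the ratios: 1.96 × 1.19 = 2.33, which corresponds to about 98%. With no ventilator effect the two models agree (signal 77% and 77%; null 3.8% and 3.8%).

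**4. Repeated looks.** With looks every 25 patients from 75 to 500 (4,000 trials, HCQ), the chance of at least one signal at OR 1.5 rises from 72–83% to 84–85%. By n=250 it rises from 37–50% to 53–55%. Any false signal rises from 5–9% to about 10%, which is also what both models give when ventilation is not prognostic.

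**5. Inefficacy.** At a conditional log OR of −0.3, the final-look inefficacy signal rate, unadjusted against adjusted, is 78% against 82% (20% ventilated, log OR 3) and 79% against 85% (30%, −2.5).

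**6. Cause.** When ventilator status has the same effect but randomization is not stratified by it, the excess width disappears (posterior SD / true SD 1.07–1.08, against 1.09 with no covariate effect; the remainder comes from the prior). Stratifying without adjusting is therefore the source.

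**7. Robustness.** With one assumed non-proportional ventilator effect, HCQ SE/SD is 1.08 (15% ventilated) and 1.14 (30%) unadjusted, and 1.00–1.01 adjusted. With 40% AZM-ineligible (30%, −1.5), signals rise from 73% to 78% (HCQ) and from 52% to 59% (AZM).

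**The case against.** The strongest reply is that the unadjusted analysis is openly declared, targets a valid marginal win ratio, and is accompanied by a pre-specified adjusted analysis with this covariate. Readers of the final report will see both. Section 8 includes 8.5, so Section 11 could be read as covering the adjusted analysis at interim looks, and Table 5 offers guidelines, not binding rules. This mitigates the final analysis. It does not settle the interim looks, where no adjusted result is named.

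Several further points stand:

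- The size rests on assumptions. In the mildest scenario the effect is small (SE/SD 1.03; HCQ signal 75% against 78%).
- At an equal false-signal rate the gain is only about 1–2 points. Because the Table 5 cut-offs are fixed and the probabilities are read at face value, the miscalibration still matters.
- Adjustment does not narrow the log odds ratio posterior. With a true conditional log OR of 0.4, 20% ventilated and ventilator log OR 3, the unadjusted mean is 0.275 with posterior SD 0.145 and true SD 0.113 (ratio 1.28). The adjusted values are 0.338, 0.148 and 0.138 (ratio 1.07). Too wide means relative to the estimate's own variability.
- A within-stratum win ratio is a different quantity: 1.37–1.38 against 1.28–1.35 marginal at OR 1.5, so the 1.25 cut-off becomes easier to reach. Standardizing an adjusted model over ventilator status might keep the marginal target; this was not simulated.
- Only the ordinal endpoint was simulated. Extending the point to mortality and durations rests on the same reasoning, without figures.

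**Conclusion.** The concern holds. The SAP randomizes within ventilator strata and then analyses as if it had not. If ventilator status is prognostic, the primary and interim posteriors overstate the uncertainty and pull the probabilities away from the Table 5 cut-offs, for efficacy, inefficacy and harm alike. The marginal point estimate is not biased.

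The excess in standard error runs from 3% to 19% in the four main scenarios and up to 32% in the most extreme case examined (40% ventilated, log OR 3). It is zero if ventilation is not prognostic. The direction is firm. The size is known only as a range, because prevalence and prognostic strength are not in the SAP. The change should be made; confidence in its practical size is moderate.

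**What to change.** - Add baseline ventilator status, with a diffuse prior, as a main effect in the Section 8.3 model. State in Section 11 that this model is used at every interim look.
- Define the primary win ratio within ventilator status by adapting the Section 8.5 definition without site. Keep the unadjusted marginal analysis as a sensitivity analysis and the site-adjusted analysis as secondary.
- Carry the term into the Section 9 models other than progression to ventilation.
- Extend the Section 8.6 check, now limited to "examining plots of empirical cumulative logits across treatment groups", to the ventilator term. State how the nonparametric fallback handles ventilator status, since Section 8.1 already reports that a non-informative nonparametric version was anti-conservative.
- Rerun the simulation behind the 14%, and confirm that the 1.25 and 0.9 cut-offs are meant for the within-stratum win ratio.

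The cost is SAP wording and one rerun simulation. No new data are needed, because Section 8.5 already plans to use the covariate. The downsides are an estimand conditional on ventilator status, cut-offs that apply to a slightly larger quantity, and a modest rise in false efficacy signals (single look from 2–3% to about 4%; repeated looks from 5–9% to about 10% per drug in these scenarios).
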